#### 1.2.8.4 Molecular and Immunologic Profiling of Tumors

A critical translational component of this trial will be the comprehensive assessment of molecular and immunologic correlates that predict response to magrolimab in tissue and peripheral blood. Accurate identification of patients most likely to respond to treatment will be paramount for the success of our precision medicine trial. Similarly, the identification of both intrinsic and acquired resistance mechanisms to magrolimab will enhance further drug development. To reach these goals, we aim to study the molecular and immunologic correlates of response with a comprehensive molecular analysis of baseline biopsies. Further, the study design will utilize a “window of opportunity” in which patients will receive magrolimab and obinutuzumab for 2 cycles prior to the triplet combination. This study design will allow us to characterize predictive biomarkers from on-treatment tissue biopsies taken during the window and at disease progression. We will assess changes in RNA expression, clonal evolution and mechanisms of resistance.

The National Cancer Institute’s (NCI) Center for Cancer Research (CCR) is uniquely positioned to execute the strong translational emphasis of this proposal. The [name] lab will perform comprehensive molecular characterization of the tumors at baseline on FFPE blocks, including whole-exome sequencing, transcriptome profiling, AffySNP6.0 and arrays for copy number abnormalities, and will explore emerging technologies such as single cell RNA sequencing. Given the influence of cells in the tumor microenvironment (TME) to tumor behavior, we aim to study the molecular evolution of both the tumor and the TME during therapy[\(94\)](#). Recent advances in genomic technologies enable the gene expression profiling at the single cell level, a distinct advantage over conventional GEP which cannot always distinguish tumor vs. non-tumor gene expression[\(95, 96\)](#). Single-cell approaches allow identification of the evolution of rare populations of tumor cells, prone to distant spread or therapy resistance, as well as identification of TME cells that may be critical for the survival of the tumor and/or those immune populations that can be harnessed to attack the malignancy. The NCI-CCR operates a single cell analysis core facility with expert staff headed by [name] within the CCR Genomics Core. This facility can take purified viably frozen cells banked from patient biopsies and prepare them, using well-validated 10X Genomics technology, for single-cell RNA sequencing. This core is directly integrated with the NCI Sequencing core facility to provide high-quality, deep-sequencing of the single cell RNA-SEQ samples, as well as ‘first-pass’ data processing and analysis. Data can then

be transferred to scientists and bio-informaticians in the [name] lab for further analysis of gene expression patterns and cellular population dynamics.

The TME within indolent lymphomas influences both response and resistance to targeted therapy. FL is a proliferation of malignant germinal center B-cells admixed with a varying proportion of nonmalignant immune cells such as T-cells, follicular dendritic cells and stromal cells. FL tumor cells in nodes retain a substantial dependence with the nonmalignant cells and other stromal elements from the TME in a pattern described as “re-education”[\(97\)](#). Interactions of FL cells with dendritic cells and macrophages allow them to survive in the germinal center environment even in the absence of an attached antigen[\(98, 99\)](#). Moreover, in some models of carcinogenesis, progression is associated with a macrophage phenotype switch with low IL-12 expression, high IL-10 expression, and low tumocidal activity and promotion of tissue remodeling and angiogenesis[\(100\)](#). Increased number of lymphoma-associated macrophages has been associated with worsened OS in patients treated with chemotherapy, but in patients receiving rituximab with chemotherapy, it was associated with improved survival[\(101, 102\)](#). Other studies have found no association of tumor-associated macrophages on prognosis[\(103\)](#). Neoplastic follicles also contain T cells, primarily CD4+, with a higher CD4:CD8 ratio in low-grade (Grade 1-2) than in Grade 3 FL[\(104\)](#). Multiple studies have associated Treg and TFH cells with clinical outcomes, but the results are inconsistent with some studies finding high Treg or high CD8+ cell numbers to be associated with favorable prognosis, and others non-significant[\(105-107\)](#).

These studies involved different patient populations and treatment regimens, and that may have contributed to discordant results. Moreover, most of these studies utilized immunohistochemistry for detecting the types of cells and the results are subject to difference between pathologists in interpreting the results. The cell types initially believed to represent a single lineage are actually many distinct subsets with distinct functions. Optical tissue imaging has revealed specialized localization of a few of these cellular subsets in FL such as lack of naïve B cells (mantle zone), presence of follicular dendritic cells in extranodal sites and absence of FDCs in diffuse areas of FL; and high prevalence of Tregs in follicular areas and absence in areas transformed to DLBCL[\(98, 104, 108\)](#). The spatial arrangement of the TME in FL varies across patients and depends on the genetic aberrations within the tumor cells as well as dependence on external stimuli for survival, proliferation, and immune escape. Conventional microscopy provides spatial information, but typically identifies cells by one or a very few markers. Hence, visualization and quantification of cellular subsets defined by complex phenotypic marker combinations is challenging. In contrast, flow cytometry provides more robust phenotypic data, but no information about spatial distribution of the various cell subsets. A combination of both these modalities would be ideal to study tumor microenvironment in indolent lymphomas.

In collaboration with [name], in the Center for Advanced Tissue Imaging (CAT-I), we have developed a lymphoma-specific antigen panel that can be assessed by a tissue imaging method called “histo-cytometry.” This strategy combines multiparameter 3D confocal imaging, spillover and deconvolution correction, identification and 3D reconstruction of specific cells of interest, and graphical data display. Histo-cytometry allows visualization, quantification, and positional analysis of diverse cell populations characterized by multiple markers directly in tissue sections. In initial studies, the histo-cytometry based cell positioning was consistent with normal biological localization of cell types in murine lymph nodes[\(109\)](#). When tissue quantitative cells subset discrimination by this method was compared with flow-cytometry based quantitation of contralateral lymph nodes in the animals, the correspondence was close to 1:1. Moreover, histo-

cytometry reliably tracked the phenotypic changes associated with T-cell activation and proliferation and was able to identify intranodal spatial distribution of all conventional dendritic cell subsets. This novel imaging technology will enable highly multiplexed, quantitative image analysis of lymph node samples and can be performed serially. We plan to explore the three-dimensional relationship of immune cells and stromal cells of interest in all indolent lymphomas using this technique. This is of particular interest to our study, as the mechanism of action of magrolimab depends on activation of innate immune system by enabling macrophage induced phagocytosis of NHL cells, and also activation of adaptive immunity by dendritic cell mediated priming of CD8+ T-cells([36](#), [37](#)). Patients will have tumor biopsies at baseline (if required, based on inadequate existing tissue), during the “window” treatment period with magrolimab and obinutuzumab, and at the time of progression. Dense phenotypic and spatial data made available by histo-cytometry at these timepoints will enable us to better understand immunological correlates of response, and resistance to treatment with anti-CD47 antibody and obinutuzumab. The diverse mechanism of action of immune checkpoint inhibitors (including magrolimab) in modulating the tumor microenvironment requires a careful assessment of the end points, such as while using functional imaging (FDG-PET). Because the TME is responsible for a significant amount of FDG uptake, agents causing immune activation may also cause an initial increase in PET activity, similarly to effects of anti-PD1/anti-CTLA4 antibodies observed in solid tumors([110](#)). Histo-cytometry will also provide additional information to distinguish immune reaction from tumor progression.

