#### 1.1.3 Exploratory Objectives

- To determine the best overall response rate (CR + PR) of 2 cycles of doublet combination therapy with magrolimab and obinutuzumab ('Window Treatment')
- To determine the rate of complete molecular remission (MRD negativity) by circulating tumor DNA (ctDNA) assay or similar assays as they become available after doublet-combination therapy with magrolimab and obinutuzumab and/or triplet combination therapy with magrolimab, obinutuzumab, and venetoclax
- To identify a mutational or gene-expression signature that predicts response to magrolimab and obinutuzumab

- To identify a mutational or gene-expression signature associated with intrinsic resistance to magrolimab and obinutuzumab
- To explore immunologic correlates of response and mechanisms of resistance to magrolimab and obinutuzumab
- To determine if ctDNA assays identify molecular relapse prior to clinical progression
- To test immunogenicity of magrolimab and to assess the effect of anti-drug antibodies (ADA) on the pharmacokinetics, pharmacodynamic markers, efficacy, and safety of magrolimab

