#### **5.3.5 DNA/RNA Sequencing**

Genomic DNA and total RNA will be extracted from tumor samples using a Qiagen All-prep kit. For individual target genes that are recurrently mutated in indolent NHL, classical Sanger sequencing will be performed on PCR amplicons, using primers surrounding the known sites of mutation. To broadly assess mutations, next generation sequencing (e.g., on an Illumina HiSeq 2000 platform) will be employed, using a paired end sequencing strategy of libraries constructed from tumor DNA. DNA will either be sequenced in its entirety from a whole genome library or will be first enriched for exonic sequences using the Agilent Sure Select system, aiming for 30X or 100X average coverage per base, respectively. The sequence fragments will be mapped back to the genome using the BWA algorithm. Of sequences overlapping a particular base pair in the genome, the percent mutant calls greater than 20% with a minimum of 25X coverage will be

considered as an arbitrary threshold for single nucleotide variants (SNVs). SNVs that are not present in the matched normal sample will be considered candidate somatic mutations.

A related technology, RNA-Seq, utilizes RNA from the tumor specimen to create a cDNA library for high-throughput sequencing. RNA-seq will be performed using Illumina kits followed by high-throughput sequencing on an Illumina HighSeq 2000 machine. The cutoffs for coverage and percent mutant calls mentioned above will also be used to identify putative SNVs. RNA sequencing will also be used to read out digital gene expression across the genome as described.

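### The bulk SNV rule (mutant reads above 20%, at least 25X) takes no account of tumor purity or clonal fraction, so baseline mutation calls miss subclones and vary with purity.

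*Combined protocol and SAP*

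**What the plan says.** Section 1.1.3 lists mutational or gene-expression signatures among the exploratory objectives, including this one: "To identify a mutational or gene-expression signature associated with intrinsic resistance to magrolimab and obinutuzumab". Section 1.2.8.4 adds clonal evolution to the translational aims: "We will assess changes in RNA expression, clonal evolution and mechanisms of resistance".

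The calling rule is in 5.3.5. At a given base it requires "the percent mutant calls greater than 20% with a minimum of 25X coverage", and this is "considered as an arbitrary threshold for single nucleotide variants (SNVs". Variants absent from the matched normal become candidate somatic mutations. Planned depth is stated as "aiming for 30X or 100X average coverage per base, respectively", that is, 30X for whole genome and 100X for exome. Bulk RNA-Seq inherits the rule: "The cutoffs for coverage and percent mutant calls mentioned above will also be used to identify putative SNVs".

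No adjustment for purity, copy number or clonal fraction is described. Section 1.2.8.4 does say that tumor content is not constant: "FL is a proliferation of malignant germinal center B-cells admixed with a varying proportion of nonmalignant immune cells".

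On timing, 1.2.8.4 and 5.1 place whole-exome sequencing, transcriptome profiling and copy-number arrays on baseline FFPE blocks. Section 5.1 repeats single-cell RNA sequencing, and plans histo-cytometry, on window and progression biopsies.

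**The concern.** A mutant-read share depends on three things: how much of the sample is tumor, what fraction of tumor cells carry the mutation, and the copy number at the site. A fixed cutoff treats all three as one. Two problems follow for the baseline signatures.

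First, a subclone that is already resistant before treatment is a natural target of an intrinsic-resistance analysis, and it is what a 20% cutoff tends to remove. Second, the same clonal mutation can be called in one patient and not in another only because the second biopsy holds more nonmalignant cells. Section 1.2.8.4 also says that the microenvironment influences response and resistance. Purity may therefore be linked both to whether a mutation is called and to whether the patient responds, and an apparent mutational signature could partly be a purity signature.

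**Working it through.** **Plan's own figure.** The 20% cutoff cannot be reproduced, because the plan gives no inputs for it. Its consequences can be computed.

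**Inputs.** From 5.3.5: share above 20%, minimum depth 25X, mean depth 30X (genome) or 100X (exome). The documents give no purity or clonal fraction, so the values below are assumptions shown over a range. The model is a heterozygous mutation in a diploid region, with binomial read sampling at a fixed depth.

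**Step 1: expected share.** Expected share = purity × clonal fraction / 2. It exceeds 0.20 only if purity × clonal fraction exceeds 0.40, so more than 40% of all cells in the sample must carry the mutation. The minimum clonal fraction is 0.40 / purity:

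| Purity | Clonal fraction must exceed |
|---|---|
| 100% | 40% |
| 80% | 50% |
| 60% | 67% |
| 50% | 80% |
| 40% or less | not attainable |

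**Step 2: probability of a call.** P(call) = P(Bin(n, share) ≥ k), where k is the smallest count above 20% of n: 7 reads at 30X and 21 reads at 100X.

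| Case | Share | 30X | 100X |
|---|---|---|---|
| Clonal, purity 60% | 0.30 | 84% | 98% |
| Clonal, purity 40% | 0.20 | 39% | 44% |
| Clonal, purity 30% | 0.15 | 15% | 7% |
| Subclone in 30% of tumor cells, purity 80% | 0.12 | 6% | 0.7% |
| Subclone in 20% of tumor cells, purity 100% | 0.10 | 2.6% | 0.08% |
| Subclone in 30% of tumor cells, purity 60% | 0.09 | 1.5% | 0.02% |

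Below the cutoff, more depth makes a call less likely, because the observed share settles closer to its expected value. Deeper sequencing therefore does not cure the problem under this rule.

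**Step 3: conditional case of a later bulk sample.** Suppose a clonal mutation is unchanged while purity falls from 60% to 30%. The probability that it is called first and missed later is P(call at 0.30) × [1 − P(call at 0.15)]:

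- 100X: 0.984 × (1 − 0.066) = 0.92
- 50X (11 reads needed): 0.921 × (1 − 0.120) = 0.81
- 30X: 0.840 × (1 − 0.153) = 0.71

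A fall from 80% to 40% gives 56% at 100X and 60% at 30X. These figures apply only if bulk sequencing is run on both samples.

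**Step 4: limit of the model.** Copy-number change or loss of heterozygosity can raise the share. With one remaining mutant copy at 40% purity, the expected share is 0.4 / (0.4 + 2 × 0.6) = 0.4 / 1.6 = 25%, not 20%. This matters because 17p deletion is among the features that can qualify MCL and CLL patients after one prior line of therapy (2.1.1.2).

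**The case against.** The strongest reply is that the rule governs only part of the plan. Sections 1.2.8.4 and 5.3.5 assign rare cell populations to single-cell methods. The blood calendar in 5.1 schedules serial ctDNA with mutational panels, and 5.3.9 plans monitoring for individual aberrations. Section 5.3.5 also plans Sanger sequencing of recurrently mutated genes. None of these carries the 20% rule. A reader might infer that the trial cannot see minor resistant clones at all; the documents do not support that. The reply stands as far as it goes. However, the single-cell work is described mainly for expression and population dynamics, no sensitivity is given for the ctDNA panels, Sanger sequencing is not shown to be more sensitive, and no section says which platform carries the clonal-evolution analysis.

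A reader might also infer from the 92% figure that responders will falsely appear to lose mutations during treatment. That too goes beyond the documents. Bulk exome sequencing and arrays are placed at baseline. Section 5.3.5 speaks only of tumor samples, so a paired bulk comparison is neither stated nor excluded, and 10.4.9 specifies no test of clonal change against response.

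Section 5.3 leaves the exact methods open until samples are ready, and 5.3.5 labels its output as candidate or putative. This allows a better rule but does not supply one. Finally, the purity values are assumed, and the statement that tumor content varies concerns FL only, while the trial also enrolls MZL, MCL and CLL.

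**Conclusion.** The point holds for bulk SNV calls on baseline tissue. Followed as written, the rule misses nearly all heterozygous diploid subclones carried by about 20% or less of tumor cells: at most 2.6% are called at 30X even with a pure sample. It also makes the call of a fully clonal mutation depend on purity, from 98% at 60% purity to 7% at 30% (100X). The mutational signatures of response and intrinsic resistance in 1.1.3 would carry both defects.

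The size rests on the assumed purities, the heterozygous diploid model and fixed depth; loss of heterozygosity or copy-number change can soften it. The false-loss figure (92% at 100X for a fall from 60% to 30%) is conditional on later bulk sequencing.

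The analysis is exploratory and descriptive. The primary safety objective, dose decisions, sample size and treatment-duration rules are untouched. This is a worthwhile, inexpensive improvement and not a threat to the trial's main conclusions.

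**What to change.** Amend 5.3.5 as follows.

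1. Keep the 20%/25X cutoff at most for first-pass discovery.
2. Call lower-share variants with an error-model somatic caller against the matched normal that is already planned.
3. At baseline, report clonal fraction adjusted for purity and copy number, using the arrays already planned in 5.3.7, and use it in the signature analyses in place of presence or absence.
4. If more than one sample from a patient is bulk sequenced, re-read every site called in any of them by its mutant and total counts, instead of re-applying the cutoff. Adjust later samples to clonal fraction only where copy-number data exist for them.
5. State which platform carries the clonal-evolution analysis.

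The cost at baseline is wording and bioinformatics time, with no new sample or assay. The downside is more low-share candidates to filter, including possible FFPE artifacts. Clonal-fraction adjustment of later biopsies would need copy-number data that the plan does not clearly provide, which is why item 4 is limited.

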#### 1.2.8.5 Use of Circulating Tumor DNA

Measurement of minimal residual disease (MRD) is not part of the standardized criteria for disease response or disease monitoring in indolent lymphomas, but many research applications are currently being developed. Multiple methods have been tested for detecting MRD in B-cell malignancies with limitations. Multiparameter flow cytometry (MFC) can easily be performed on peripheral blood or bone marrow as a marker of MRD, but this method may not be sensitive enough in diseases that do not routinely circulate([111](#)). Even in CLL, where MFC reliably quantitates CLL cells to the level of 10^-5, NGS-based approaches appear to have a lower limit of detection and can assess clonal evolution([112](#)).

The tumor-specific component of cell-free DNA, known as circulating tumor DNA (ctDNA), is a highly sensitive and specific marker of all B-cell malignancies and is an emerging technology designed to overcome the fundamental limitations of response assessment based on imaging scans. A secondary objective of this trial is to utilize ctDNA as a marker of MRD and compare the results to the standard assessment of disease response and monitoring for disease recurrence after therapy stops. Many patients who achieve a CR based on conventional criteria will have the persistence of MRD below the detection limit of imaging scans highlighting the need for more sensitive measures([113](#), [114](#)). As a measure of the depth of response, we will define the complete molecular remission rate after triplet combination therapy. Further, we will analyze the predictive ability of ctDNA for predicting disease relapse when measured at pre-planned timepoints after therapy stops.

Various technologies exist for the detection and analysis of ctDNA. Malignant B cells possess a unique DNA sequence that encodes its rearranged immunoglobulin variable, diversity, and joining (VDJ) genes. Using universal primers in combination with next-generation sequencing (NGS), this unique VDJ sequence can be utilized as a quantitative biomarker of disease([114](#)). This technique requires identification of rearrangements in tumor tissue (a clonotype), which can then be followed in peripheral blood. In a study comparing NGS-based method with RQ-PCR in MCL,

49 out of 55 (89%) patients had a clonotype detected by NGS compared to 45 out of 55 (82%) by RQ-PCR([115](#)). Clonotypes identified by both techniques were identical in 96% of the cases. NGS demonstrated at least the same level of sensitivity as RQ-PCR, without the need for patient-specific reagents. Technologies have since evolved, and in a more recent study, tumor clonotypes were successfully detected at baseline and followed serially in 96% of patients with MCL([116](#)). Of note, in all patients who had baseline formalin-fixed paraffin embedded (FFPE) tissue available, one or more clonotypes were detected. A linear association was demonstrated between baseline quantitative ctDNA levels and tumor burden as measured by total metabolic tumor volume (TMTV). More importantly, ctDNA was able to provide an early readout of sensitivity to therapy as decrease in levels as early as after 1 cycle of treatment with chemotherapy and targeted agents (EPOCH-R plus bortezomib) was shown to be associated with improved PFS. The utility of this assay has also been preliminarily tested in FL([117](#)). In a randomized study of FL patients, a subset of patients had tumor and plasma samples available for analysis for VDJ sequences. At least one tumor clonotype could be detected in 29 patients (85%) in the diagnostic tumor sample. ctDNA corresponding to the clonotypes were detected in 25/29 (86%) of the matched plasma samples.

We will use a modern ctDNA platform that combines universal PCR primers for the variable-diversity-joining (VDJ) region of the immunoglobulin receptor with next-generation sequencing (NGS) technologies (i.e., clonoSEQ®)([118](#)). This ctDNA assay is highly tumor-specific and can be used as a method for disease detection at the molecular level in a variety of B-cell malignancies([115](#), [117](#), [119](#)). Since the clinical utility of achieving complete molecular remission is unknown, this will be an exploratory endpoint. Lastly, we aim to study the utility in using ctDNA as an active surveillance tool after therapy has been completed to determine the kinetic relationship between ctDNA reappearance and clinical relapse. These data could inform future studies that initiate intervention on the basis of molecular relapse. Altogether, ctDNA will be used in this study as a non-invasive method to monitor tumor response kinetics during therapy, define the depth of response, and as a surveillance tool for early disease detection after therapy cessation.

